Protocol title:

Feasibility of using daily Humidified Nasal High-flow with Oxygen during Sleep and/or Daytime in Hypercapnic COPD patients following recent (< 12 wks.) hospitalization for AECOPD for 90 days

NCT03221387

Date: 10/06/2017

1) Abstract of the study

Humidified Nasal High-flow with Oxygen (HNHF-O2) therapy has been reported to have acute beneficial effects in patients with hypoxemic respiratory failure. HNHF-O2 may be beneficial in patients with COPD and chronic impairments in gas exchange, both hypoxemia as well as hypercapnia. HNHF-O2 may decrease work of breathing, reduce dyspnea, improve airway humidification, and potentially stabilize or reduce carbon dioxide levels. However, there is limited data showing the chronic effects of HNHF-O2 in patients with hypercapnic respiratory failure, specifically those discharged to home following hospitalization for an acute exacerbation. Data that demonstrates that HNHF-O2 is well tolerated, and stabilizes or improves gas exchange long term in patients with COPD is lacking. Similarly, data that demonstrates that this therapeutic regimen is feasible to provide to patients in the home environment are lacking. This is an open-labeled pilot study of thirty patients to determine the safety and feasibility of using the device in the outpatient management of patients with COPD.

2) Protocol Title

Feasibility of using daily Humidified Nasal High-flow with Oxygen during Sleep and/or Daytime in Hypercapnic COPD patients following recent (< 12 wks.) hospitalization for AECOPD for 90 days

3) IRB Review History

Not applicable

4) Investigator

[name]

5) Objectives

To assess the feasibility of using daily home HNHF-O2 during sleep and/or daytime in hypercapnic COPD patients following recent (< 12 weeks) hospitalization for AECOPD for 90 days.

6) Background

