current use (\leq 4 weeks of study entry) of any PAP-therapy (e.g., CPAP or NPPV); sleep apnea as follows: STOPBang scores \geq 5 or STOPBang score \geq 2 plus BMI $>$ 35 kg/m²; or Berlin questionnaire scores suggesting high likelihood of sleep apnea with increased risk of sleep-related accident (e.g., occupation as a commercial driver or pilot); or excessive daytime sleepiness (i.e., either of High (>15) score on the Epworth Sleepiness Scale or “fall asleep” accident or “near miss” accident in prior 12 months).

c) Local Number of Subjects

Thirty subjects will be accrued locally for this study.

We expect few screen failures.

d) Study-Wide Number of Subjects

If this is a multicenter study, indicate the total number of subjects to be accrued across all sites. – Not applicable.

e) Study Timelines

- Subjects will be followed for 90 days with regular telephone follow-up and clinic visits throughout.
- Subjects will be enrolled over a period of 12 months.
- The investigators will complete the data analysis approximately 18 months after the first subject is enrolled.

f) Study Endpoints

The primary endpoints of this study are the feasibility of oxygen therapy by HNHF-O2 at home over a 90-day period in terms of tolerance and hours of use. Descriptive statistics will be used to characterize the patient population in terms of demographic factors and severity of airflow obstruction. Changes in PaO₂, PaCO₂ and pH across the days will be done by analysis of variance. The effect of baseline PaCO₂ on change in PaCO₂ with HNHF-O2 therapy will be analyzed as an independent effect on change in PaCO₂ levels with HNHF-O2. Changes in respiratory rate, heart rate, blood pressure accessory muscle use will also be assessed by analysis of variance. Patient tolerance and side effects will also be measured across days of use per patient and across days in all patients as group trends. Hours of use per device log and per patient diary will be independently analyzed and compared to one another. The impact on change in exacerbation frequency and severity will be analyzed. Changes in spirometry, 6MWD, GOLD grade and class and BODE scores prior to and after 90 days of HNHF-O2 will be analyzed.

g) Procedures Involved in the Human Research

[figure not shown]
An overview of the study is provided in the figure below.

Outpatient HNHF-O2 Protocol

Version 3.0

10/06/2017

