Feasibility of using daily home HNHF-O2 during Sleep and/or Daytime in Hypercapnic COPD patients following recent (< 12 wks.) hospitalization for AECOPD for 90 days

¹ > 40 yrs. Age and Hospitalized for AECOPD; able to sign IC and willing to do tests

² vital signs, respiratory patient discomfort, Likert scale for clinical improvement, dyspnea (modified Borg Score, mMRC) ABG 5 minutes after inspiring O₂ to maintain SaO₂ >90%, spirometry, 6 MWT, questionnaires (CAT, SGRQ), set baseline diary for respiratory symptoms

³ Inquire about any problems and assess for adherence, troubleshoot

⁴ vital signs, respiratory patient discomfort, Likert scale for clinical improvement, dyspnea, side effects of HNHF-O₂, and review daily electronic diary of respiratory symptoms

⁵ Same as #2

Patients who have had a recent COPD exacerbation (<12 weeks since discharge) accompanied with respiratory failure who meet the above inclusion criteria will be considered for participation in the study.

Once informed consent has been obtained patients will be given the opportunity to participate in the sleep substudy until the enrollment goal of ten subjects has been achieved. A separate protocol and consent form has been submitted for this study. The following procedures will be performed as part of the main study:

Outpatient HNHF-O2 Protocol

Version 3.0

10/06/2017

Test	Visit 1 Screening	Visit 1a Baseline	Visit 2 Clinic Placed on HNHF-O2	Visit 3 Phone Call Day 1	Visit 4 Phone call Day 3 ± 3	Visit 5 Clinic Day 7 ± 5	Visit 6 Phone call Day 17 ± 3	Visit 7 Clinic Day 28 ± 5	Visit 8 Phone call Day 37 ± 3	Visit 9 Clinic Day 49 ± 5	Visit 10 Phone call Day 58 ± 3	Visit 11 Clinic Day 70 ± 5	Visit 12 Phone call Day 80 ± 3	Visit 13 Clinic Day 90 ± 5
Screen	X													
Informed Consent	X													
History & Physical		X				X		X		X		X		X
Pregnancy test for women of childbearing potential		X												
Arterial blood gas◆		X	X											x
Pre- and Post- Bronchodilator Spirometry		X												X
6 minute walk distance		X												X
mMRC Questionnaire		X ²												
Borg Questionnaire		X ²	X			X		X		X		X		X
Assess Accessory Muscle use		X	X			X		X		X		X		X
Assess subject comfort		X	X			X		X		X		X		X

Outpatient HNHF-O2 Protocol

Version 3.0

10/06/2017

Test	Visit 1	Visit 1a	Visit 2	Visit 3	Visit 4	Visit 5	Visit 6	Visit 7	Visit 8	Visit 9	Visit 10	Visit 11	Visit 12	Visit 13

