At baseline, patients will have measurement of vital signs (heart rate, respiratory rate and blood pressure), dyspnea (modified Borg score, mMRC) arterial blood gas after 5 minutes of inspiring supplemental oxygen to keep $\text{SaO}_2 > 90\%$, and use of accessory muscles of ventilation. Patients will have spirometry performed pre-and post-bronchodilator administration. Patients will have assessment of their current respiratory health by completing CAT, mMRC and SGRQ questionnaires. A detailed history of their exacerbation frequency and severity will be obtained. Patients will perform a 6-minute walk test. Patients GOLD grade and group will be classified and patients BODE scores will be calculated.

Patients will be queried regarding the presence and magnitude of complaints of cough and sputum production by using a daily electronic diary for a 2-week period of run in. After the 2-week run-in period the patient will be scheduled to return to initiate HFNC with oxygen therapy.

Electronic daily diary of respiratory symptoms.

- ❖ Breathlessness (Modified Borg Scale)
- ❖ Sputum Quantity, Color, and Consistency
- ❖ Peak Flow Measurements
- ❖ Presence of Temperature Over 100°F
- ❖ Presence of Any Cough, Wheeze, Sore Throat or Nasal Congestion

Outpatient HNHF-O2 Protocol

Version 3.0

10/06/2017

Patients will be seen in clinic and instructed in the use of HNHF-O2 and its proposed benefits. The necessity of compliance and adherence to the treatment plan will be emphasized.

Following the outpatient clinic visit, patients will be set up at home using an established home vendor for respiratory equipment. Patients will continue to report their daily respiratory symptoms via the electronic diary.

Post placement on optimal dose of HNHF-O2 therapy, subjects will be called the next day to determine if there were any problems.

Patients will report to clinic at baseline and then 7 ± 2 , 28 ± 5 , 49 ± 5 , and 70 ± 5 days for the following assessment:

- Measurements of vital signs (heart rate, respiratory rate and blood pressure)
- Respiratory patient-discomfort and dyspnea assessed using an unmarked 100 mm visual analogic scale from “no discomfort” to “maximal imaginable discomfort”
- Likert scale model indicating marked improvement (+2), slight improvement (+1), no change (0), slight deterioration (-1) and marked deterioration (-2)

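### The blood-gas analysis names no reference visit or contrast, so a shift during the run-in before the device could by itself make the test across days significant

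*Combined protocol and SAP*

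**What the plan says.** The test is specified in one sentence, in 10(f) and again in 10(i): changes in the three gas measures "across the days will be done by analysis of variance". It does not list visits, name a reference visit or contrast, or say that the measures are repeated within patients. The sentence after it takes baseline PaCO₂ as a predictor and speaks of PaCO₂ change under HNHF-O2.

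In the schedule table of 10(g), the row "Arterial blood gas" is marked three times: at Visit 1a (Baseline), in the column headed "Visit 2 Clinic Placed on HNHF-O2", and at Visit 13 (Day 90). The text of 10(g) puts the baseline measurements first, then a "daily electronic diary for a 2-week period of run in", and then: "After the 2-week run-in period the patient will be scheduled to return to initiate HFNC with oxygen therapy".

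The patients are described in 10(g) as "Patients who have had a recent COPD exacerbation (<12 weeks since discharge) accompanied with respiratory failure". The abstract gives the design: "This is an open-labeled pilot study of thirty patients". There is no comparison group. The primary endpoints in 10(f) are tolerance and hours of use, and 10(i) says that the study does not test efficacy.

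The gas conditions differ between places in 10(g). The baseline paragraph and note 2 to the overview figure have the baseline gas taken after five minutes on supplemental oxygen. The footnote to the gas row and the arterial blood gas paragraph under study procedures have gases taken on room air, 20 minutes off the device. The footnote allows 2 L of oxygen if the participant desaturates.

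**The concern.** An overall analysis of variance on three occasions asks whether any of the three means differs from the others. One way for that to happen is a difference between Visit 1a and Visit 2. By the order in 10(g), the device is not in use over that interval, and the patients may still be recovering from a recent hospitalised exacerbation. A significant result would not show whether the change came before or after the device started.

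Modelling the within-patient correlation correctly does not remove this problem. Neither does reducing the analysis to Visit 1a against Visit 13, because that difference contains the run-in as well.

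What is at stake is interpretation. The abstract says that long-term gas-exchange data are lacking in these patients, so readers will look at the PaCO₂ result. A shift that preceded the device could be read as a change on therapy. The trial already schedules a sample that could separate the two intervals, but the plan does not say that it will be used that way.

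**Working it through.** **The plan's own figures.** None concerns the gas analysis. The only computed number is the sample size in 10(i): ln(1 − 0.95)/ln(1 − 0.10) = 28.43, which reproduces the printed 28.4. (The prose beside it says 15%, which would give 18.43; that is a separate matter.) It concerns withdrawal for intolerance.

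**Inputs**
- From the documents: three gas occasions (10(g) table); a two-week run-in before the device (10(g) text); 30 evaluable patients (10(i)); no control arm (abstract).
- Assumed, because the documents give no value: alpha 0.05; within-patient SD of PaCO₂ s = 4 mmHg, with a range of 3 to 6; pre-device fall d of 0 to 4 mmHg; a one-factor repeated-measures analysis with equal correlations.
- Scenario: means (d, 0, 0) at Visits 1a, 2 and 13, so that nothing changes after Visit 2.

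**Step 1. Three-occasion test.** The grand mean is d/3, so the squared deviations sum to (2d/3)² + 2(d/3)² = 2d²/3. The noncentrality is λ = 30 × (2/3) × d²/s² = 20d²/s², on F(2, 58). With s = 4, λ is 1.25, 5, 11.25 and 20 for d = 1, 2, 3 and 4. Percentage of trials significant:

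| SD (mmHg) | d = 1 | d = 2 | d = 3 | d = 4 |
|---|---|---|---|---|
| 3 | 23.6 | 74.2 | 98.0 | about 100 |
| 4 | 15.0 | 48.2 | 84.1 | 98.0 |
| 5 | 11.2 | 32.5 | 64.4 | 88.7 |
| 6 | 9.2 | 23.6 | 48.2 | 74.2 |

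With d = 0 every entry is 5. With 20 patients and s = 4 the row is 11.3, 32.9, 65.1 and 89.1. A simulation of 20,000 trials with n = 30 gave 5.1%, 15.0%, 48.7% and 83.9% at drifts of 0, 0.25, 0.5 and 0.75 SD, in agreement with the formula.

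**Step 2. Visit 1a against Visit 13 only.** This is a paired t test with difference SD s√2 and 29 degrees of freedom. With s = 4 it is significant in 15.5%, 46.5%, 80.2% and 96.3% of trials for d = 1 to 4. The fault is nearly the same size.

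**Step 3. Visit 13 minus Visit 2.** In the same simulated data this contrast was significant in 4.7% to 5.0% of trials at every drift from 0 to 1 SD. Its standard error is s√(2/30) = 4 × 0.258 = 1.03 mmHg. Under the assumed equal correlations this is the same as for Visit 13 minus Visit 1a, so no precision is lost.

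**Step 4. Recovery that continues after Visit 2.** The Visit 13 minus Visit 2 contrast then rejects too often as well: 15.5% for a further 0.25 SD and 46.5% for a further 0.5 SD (1 and 2 mmHg at s = 4).

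**Step 5. If pairing were ignored.** With a between-patient SD twice the within-patient SD, an unpaired analysis of variance was significant in 0.4% of trials at a drift of 0.5 SD and 21% at 1 SD. That form rarely rejects, but it would also rarely detect a real change.

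**The case against.** The strongest reply is that the plan never says Visit 1a enters the test. Visits 1a and 2 carry no day number; numbered days begin after placement, and 10(f) also speaks of days of use. Nothing rules out contrasts within the analysis of variance. This stands in part: the inclusion of Visit 1a is inferred. But of the three gas visits only Visit 13 has a day number, so a change in gases needs at least one of the other two, and the plan does not say which.

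A reader might infer that the plan commits itself to crediting any gas change to the device. The text does not support that. The analysis-of-variance sentence attributes nothing, and the reference to HNHF-O2 belongs to the next sentence, on baseline PaCO₂ as a predictor.

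The sizes also rest on assumptions. Entry can be as late as 12 weeks after the exacerbation, so little recovery may remain for some patients, and a small drift gives a small inflation.

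Two objections to using Visit 2 as the reference stand. The column heading and the condition of 20 minutes off the device leave open whether the Visit 2 gas follows first use. If it does, Visit 2 minus Visit 1a includes some exposure, and Visit 13 minus Visit 2 would subtract any lasting early effect. Also, if the Visit 1a gas is taken under a different oxygen condition, that alone would shift its values.

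**Conclusion.** The concern holds as a fault in a secondary analysis. On the natural reading, the stated test cannot separate a run-in shift from a change after the device starts, although the scheduled samples could. With 30 patients, a repeated-measures model and a within-patient SD of 4 mmHg, the test is significant in about 15%, 48% and 84% of trials for pre-device falls of 1, 2 and 3 mmHg, and in 5% with no drift. The drift, the SD and the model form are all assumptions.

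Two stronger conclusions are tempting. The first is that 84% is this trial's false-positive rate. It is not: it is one cell of an assumed range, and the documents give no recovery size. The second is that Visit 13 minus Visit 2 would isolate the effect of the device. It removes the run-in shift only, and its 5% holds only if recovery stops at Visit 2. In a single-arm study, later recovery cannot be separated from the therapy.

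The primary feasibility endpoint is not affected.

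**What to change.** **In 10(f) and 10(i):** make the within-patient change Visit 13 minus Visit 2, with a 95% confidence interval, the main result for PaO₂, PaCO₂ and pH. Report Visit 2 minus Visit 1a beside it as the run-in change. An overall test across the three visits may stay, but should not be the basis for any statement about change with HNHF-O2.

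**In 10(g):** state whether the Visit 2 gas is drawn before first placement. Visit 2 is a clean pre-device reference only if it is; if not, say so as a limitation. The passages on the baseline gas condition (supplemental oxygen in the baseline paragraph and figure note, room air off the device in the table footnote and study procedures) must be reconciled, so that the three samples can be compared.

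**As a stated limitation:** recovery after Visit 2 remains confounded with the device because there is no control arm.

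**Cost:** no added samples or visits, since all three gases are already scheduled. The changes are to wording, plus a clear statement to sites of when and under what condition each gas is drawn. The downside is that the wider change from Visit 1a to Visit 13 is no longer the headline.

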In order to reduce the risk of contamination and extend the life of the tubing and patient interface it is recommended that the user clean the device at specified intervals. The patient interface should be washed in tap water and reconnected to the heated breathing tube. Thereafter, the device should be run in drying mode. This process takes about 90 minutes to complete and should be performed daily. On a weekly basis the heated breathing tube should be removed along with the patient interface and both washed in warm water with a mild detergent. The outside of the device should be wiped clean with a damp cloth. The inside of the heated breathing tube connection port should be cleaned with a low-lint cloth with mild dishwashing detergent.

The patient has the option to not receive supplemental oxygen during each of these cleaning procedures or to receive supplemental oxygen via a standard nasal cannula.

All supplies necessary for the maintenance of the device will be provided to the subject at no cost to them.

Study procedures:

History and physical exam, vital signs. These are all procedures routinely performed as standard of care.

Lung function testing (spirometry). Pre- and post-bronchodilator testing (spirometry) will be performed according to ATS standards. The bronchodilator

Outpatient HNHF-O2 Protocol

Version 3.0

10/06/2017

medication (albuterol) opens up the airways and will be used in lung function testing. This medication is often used to treat people with COPD. Spirometry will be performed by experienced study personnel.

Arterial blood gases. Arterial blood gases will be obtained from the radial artery in the wrist by experienced personnel. Blood gases will be obtained on room air after the patient has been off the Airvo device for 20 minutes.

6 minute walk test. Subjects will be asked to walk as far as they can for 6 minutes while receiving supplemental oxygen. Testing will be supervised by experienced study personnel with access to emergency medicine such as sublingual nitroglycerin, aspirin and albuterol.

Dyspnea questionnaires, accessory muscle use, and comfort assessments.

The Borg dyspnea questionnaire and mMRC are short questionnaires that can be completed in a minute or two. These questionnaires are included with this submission. Use of accessory muscles requires only subject observation.

Subject comfort assessments are also provided with this submission and can be completed in a minute.

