All data will be stored on the REDCap website and on password protected files on password protected computers located on the 7th floor of the Kresge Building. This is an area with access restricted to study personnel.

j) Confidentiality

All data will be stored on the REDCap website. The site is part 11 compliant. All study personnel have been trained in human subjects protections and good clinical practices. Study data will only be accessible to study personnel via password protected websites and computer terminals.

k) Confidentiality

All data will be stored on the REDCap website. The site is part 11 compliant. All study personnel have been trained in human subjects protections and good clinical practices. Study data will only be accessible to study personnel via password protected websites and computer terminals.

l) Provisions to Monitor the Data to Ensure the Safety of subjects

This study utilizes an FDA-approved device for the delivery of warmed humidified gases for a medical indication included in the 510(k) approval letter. As such, and because of the limited enrollment in this trial, there is no need for a data and safety monitoring board. Monitoring of the study will be done by the principal investigator on a routine (monthly) basis in conjunction with the study sponsor and the Director of Research at the Temple Lung Center. All adverse events will be reviewed with particular attention paid to those subjects who discontinued use of the device and those where oxygen therapy needed to be intensified in order to maintain adequate oxygenation.

m) Withdrawal of Subjects

Subjects may discontinue participation in the study at any point and for any reason. This decision will not be held against them in any way. If a subject decides to withdraw, the physician will assess their clinical condition and determine the best course of action for the subject. This may include alternative methods of oxygen administration. Any data that is collected up to the point of subject withdrawal will be retained for analysis.

11) Risks to Subjects

History and physical exam, vital signs. These are all procedures routinely performed as standard of care and are not associated with any adverse effects.

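### Serial measurements on the same patients are assigned to analysis of variance with no patient term and no way to use incomplete records; a mixed model on all available visits should be named instead

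*Combined protocol and SAP*

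**What the plan says.** Section 10 f) (Study Endpoints) states that changes in PaO2, PaCO2 and pH "across the days will be done by analysis of variance". The next outcomes get the same method: "Changes in respiratory rate, heart rate, blood pressure accessory muscle use will also be assessed by analysis of variance". Section 10 i) (Data Management) repeats both sentences and adds nothing about the type of ANOVA, a patient effect, the covariance, or missed visits.

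The data are serial. In the schedule table, the row "Arterial blood gas" is marked at Visits 1a, 2 and 13: three times. Vital signs follow the clinic visits in section 10 g): "Patients will report to clinic at baseline and then" at days 7, 28, 49 and 70, with day 90 listed separately, which makes six. Accessory muscle use is marked at seven visits. Its recording scale is not given; the procedures text says only "Use of accessory muscles requires only subject observation".

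Section 10 m) (Withdrawal of Subjects) says: "Any data that is collected up to the point of subject withdrawal will be retained for analysis". The primary endpoints are elsewhere: "feasibility of oxygen therapy by HNHF-O2 at home over a 90-day period in terms of tolerance and hours of use".

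**The concern.** With repeated measurements in one group, the error variance for a change over time depends on how the analysis treats the patient. The plan leaves this open, and each of the two usual ways of carrying out its wording has a cost.

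- **One-way ANOVA with day as the factor.** Stable differences between patients go into the error term. The test becomes conservative, and a real shift in PaCO2 can pass as no change.
- **Classical repeated-measures ANOVA.** Patients are compared with themselves, but standard software needs a complete row and omits any patient with a missed visit. Those who stop early because they do not tolerate the device are likely to lack Day 90, so the result may lean towards those who did well.

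The abstract says that long-term evidence on gas exchange with this therapy is lacking, and section 10 f) plans a specific analysis of baseline PaCO2. A false null, or a result from completers only, could misinform a later trial. An unspecified model can also be chosen after the data are seen.

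**Working it through.** **The plan's own figure.** There is no power statement for these outcomes. The one computed figure is 28.4 subjects, and ln(0.05)/ln(0.9) = 28.4 reproduces it. It concerns seeing at least one withdrawal for intolerance and says nothing about PaCO2 or vital signs.

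**Inputs from the documents.** 30 evaluable patients, one arm, three blood gases, six vital-sign visits.

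**Assumed, because the documents give no values.** 5% F test; equal correlation ρ between any two visits; a shift of 0.4 SD, where SD is the total SD at one visit; visits missed at random.

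**Step 1: within-patient test, three blood gases, complete data.** Let the means be (0, 0, 0.4) SD. The sum of squares about their mean is 0.4² × 2/3 = 0.1067. The noncentrality is λ = n × 0.1067/(1 − ρ), with 2 and 58 df.

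- ρ = 0.7: λ = 3.2/0.3 = 10.67, power 0.82.
- ρ = 0.5: λ = 3.2/0.5 = 6.4, power 0.59.

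**Step 2: one-way test on the same data.** The error mean square (87 df) estimates the full variance, 1. With no change, the day mean square has expectation 1 − ρ, so F centres near 0.3 or 0.5 instead of 1.

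| ρ | One-way power | Within-patient power | One-way type I error |
|---|---|---|---|
| 0.5 | 22% to 24% | 58% to 60% | about 0.3% to 0.4% |
| 0.7 | 16% to 17% | 82% to 83% | below 0.1% |

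Ranges show the spread between closed-form and simulated values.

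**Step 3: sensitivity to the assumed shift.** Here the shift is present at both later blood gases and ρ runs from 0.3 to 0.9. One-way power is at most 0.14 for 0.3 SD, 0.32 to 0.46 for 0.5 SD, and 0.82 to 0.94 for 0.7 SD. The harm is therefore greatest for small and moderate changes.

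**Step 4: complete-case repeated-measures ANOVA against all available data.** ρ = 0.7. The shift is 0.4 SD at Day 90 for blood gases, and a linear rise to 0.4 SD for vital signs. With baseline complete, the expected number of complete records is 30 × (1 − m)^(k − 1), for k visits and missed rate m.

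| Outcome | Missed per visit | Complete records | Complete-case power | All-data power |
|---|---|---|---|---|
| Blood gases, k = 3 | 5% | 30 × 0.95² = 27.1 | 76% | 78% |
| Blood gases, k = 3 | 10% | 30 × 0.90² = 24.3 | 72% | 76% |
| Vital signs, k = 6 | 5% | 30 × 0.95⁵ = 23.2 | about 58% | about 70% |
| Vital signs, k = 6 | 10% | 30 × 0.90⁵ = 17.7 | about 43% | about 68% |

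The power columns are simulated, and separate runs agree to within about 3 points. Visits were dropped at random, so these figures show loss of precision only. Bias from selective dropout was not quantified.

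**The case against.** The strongest reply is that the plan has committed neither error. It speaks of changes across days in a single-arm study, which fits repeated-measures ANOVA at least as well as one-way ANOVA. With complete data, the 82% in step 1 is the power of repeated-measures ANOVA itself, a method that the wording already allows. This stands. A reader might infer that the plan prescribes an uncorrelated-data ANOVA, that it drops anyone with a missed visit, or that a real PaCO2 change will probably be missed. The documents say none of these. The last holds only under the one-way reading and for changes up to about 0.5 SD; under the repeated-measures reading the loss for PaCO2 is small.

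A reader might also see a contradiction with section 10 m). There is none, since no complete-case rule exists for it to contradict. Its statement on retaining data points towards using incomplete records but does not name a method that does so.

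Three further limits stand. The one-way error is conservative, so it would not create a false claim of benefit. That accessory muscle use is present/absent or graded is plausible but not stated. And section 10 i) says that this is not an efficacy trial.

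What remains is that the text permits a badly inefficient analysis and a completers-only analysis, and does not name the one that avoids both.

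**Conclusion.** The point holds as under-specification with a measurable cost, and it should be fixed. Under the one-way reading the cost is large for both blood gases and vital signs. Under the complete-case reading it is 2 to 4 percentage points of power for blood gases, and about 12 (5% missed) to 25 (10% missed) for vital signs over six visits, with possible bias if patients who stop early do worse.

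These sizes rest on assumed SD, correlation, effect and missed-visit rates, on equal correlation between visits, and on 30 evaluable patients. Importance is moderate: the primary endpoints, tolerance and hours of use, are untouched.

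**What to change.** In sections 10 f) and 10 i), replace the ANOVA wording for blood gases and vital signs with a linear mixed model: visit as a categorical fixed effect, patient as a random effect, restricted maximum likelihood, all available visits. Report the Day 90 minus baseline contrast with its 95% CI.

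For the six-visit measures a random patient effect is preferable to an unstructured covariance, which would need 6 × 7/2 = 21 parameters from 30 patients.

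State how accessory muscle use is recorded. If it is present/absent or graded, use the binary or ordinal counterpart with a patient effect.

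The cost is a few sentences in each section, with no new patients, visits or data. The small downside is that the model assumes missed visits are missing at random; the plan should say so.
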